The primary estimand for the study is the proportion of CRESS responders on ≥ 3 of 5 items at week 24 in efgartigimod IV compared to placebo, considering the participant who discontinued study treatment or used any prohibited	Efgartigimod or placebo, taking into account study treatment discontinuation and/or prohibited concomitant medication.	Efgartigimod or placebo in the scenario where study treatment discontinuation and/or prohibited concomitant medication would not have occurred.
medications.	Population  Adult participants with pSS, per ACR/EULAR 2016 classification criteria, with at least a moderate level of systemic disease activity (ESSDAI ≥ 5) as defined by Inclusion and Exclusion criteria.	Population  Adult participants with pSS, per ACR/EULAR 2016 classification criteria, with at least a moderate level of systemic disease activity (ESSDAI ≥ 5) as defined by Inclusion and Exclusion criteria.
	Variable (endpoint)Proportion of CRESS responders on ≥ 3 of 5 items at week 24.	Variable (endpoint)  Proportion of CRESS responders on ≥ 3 of 5 items at week 24.

Document:

Author: Version Number: V2.0

Version Date: 31JAN2024
Reference: CS\_WI\_BS005

Effective Date: 01Nov2021

Template No.: CS\_TP\_BS016 Revision 7

Statistical Analysis Plan

Page 17 of 78

Intercurrent events (Composite Variable Strategy)  • Early withdrawal of study treatment • Use of any prohibited concomitant medications	Intercurrent events (Hypothetical Strategy strategy).  • Early withdrawal of study treatment • Use of any prohibited concomitant medications
Summary measure  The proportion of responders and its 95% Wilson score CI will be calculated using binomial distribution for treatment and placebo. Also, CMH will be used  The participants with ICEs will be considered as Non-Responders.	Summary measure  The proportion of responders and its 95% Wilson score CI will be calculated using binomial distribution for treatment and placebo. Also, CMH will be used.  If the planned hypothetical approach is not feasible due to data sparsity, then data will be analyzed as observed.

Abbreviations: ICE= Intercurrent Event, CI= Confidence Intervals.

Where the strategies are described as follows in the sequence, these strategies will be applied:

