#### For the supplementary estimand:

 Document:
 Version Number:
 V2.0

 Author:
 Version Date:
 31JAN2024

 Template No.:
 CS\_TP\_BS016 Revision 7
 Reference:
 CS\_WI\_BS005

Effective Date: 01Nov2021

Statistical Analysis Plan

Page 18 of 78

Hypothetical strategy: Any early discontinuation or taking prohibited concomitant medication is observed- then the assessment will be set to missing and the missing binary outcomes will be imputed, assuming that they are missing at random. The aim of hypothetical strategy is to address the effect in an alternative hypothetical setting where subject neither discontinued or no prohibited concomitant medication available.

If the planned hypothetical approach is not feasible due to data sparsity, then available data occurring on or after ICEs will be analyzed as observed (Treatment policy). The reasoning of treatment policy is to estimate the CRESS response based on the available data and data will be analyzed as it is (regardless of the intercurrent event occurring).

For both main and supplementary estimand, additional sensitivity analysis will be performed using CMH considering IgG as stratification factor.

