#### 6.6. Statistical Tests

The default significance level will be 5%; CIs will be 95% and all tests will be two-sided, unless otherwise specified in the description of the analyses. P-values for comparing treatment groups should be interpreted as supportive summary statistics.

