Analysis Methodology:

The SAS procedure MI will be used and the details of MI procedure will be stated in the dataset specification document. The missing binomial outcomes will be imputed by multiple imputation method with the assumption of monotone missing pattern and logistic regression method. Multiple imputations would be conducted based on CRESS response (Yes/No). To reduce the sampling variability from the imputation process, 500 datasets will be generated.

Here in this case the numerator will include all the participants which are responders (imputed and actual responders) and the denominator will include all participants in FAS population.

In the estimation step, separate analysis will be performed using the statistical method mentioned for the primary endpoint statistical analysis.

Because the imputation of missing data is a key aspect to the analysis of the data, explicit details regarding this imputation are provided via sample SAS code that is intended to demonstrate the application of these strategies. Minor alterations to SAP code may be performed.

Example code for imputation of binary outcome which will be used for imputation by logistic regression is as follows:

Document:

Author:

Version Number:

V2.0

Template No.: CS TP BS016 Revision 7

Version Date: 31JAN2024

[figure not shown]
Reference: CS WI BS005

Effective Date: 01Nov2021

Statistical Analysis Plan

[figure not shown]
Page 45 of 78

Statistical Analysis Plan

Page 46 of 78

[figure not shown]

Effective Date: 01Nov2021

Statistical Analysis Plan

Page 47 of 78

The values obtained from back transformed dataset, will be used for reporting Unadjusted Odds Ratio and CIs.

If the planned hypothetical approach is not feasible due to data sparsity, then available data occurring on or after ICEs will be analyzed as observed (treatment policy). In this case, the numerator will include all the participants which are responders (actual responders only) and the denominator will be participants in EAS population.

Missing data unrelated to ICEs, will not be imputed.

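### Supplementary estimand: a week 24 CRESS outcome missing without an intercurrent event is not imputed but stays in the all-FAS denominator, so it counts as non-response

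*SAP*

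**What the plan says.** SAP section 2, Table B defines a main estimand (composite strategy, ICE means non-responder) and a supplementary one (hypothetical strategy). The ICEs are early withdrawal of study treatment and use of prohibited medication. Both estimands carry the same summary measure: "The proportion of responders and its 95% Wilson score CI will be calculated using binomial distribution for treatment and placebo". A Cochran-Mantel-Haenszel (CMH) analysis is added.

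Under the supplementary estimand, when an ICE occurs, "the assessment will be set to missing and the missing binary outcomes will be imputed, assuming that they are missing at random". SAP 14.1.1 gives the method:

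- Model: "The missing binomial outcomes will be imputed by multiple imputation method with the assumption of monotone missing pattern and logistic regression method".
- Number of imputations: "To reduce the sampling variability from the imputation process, 500 datasets will be generated".
- Analysis: "In the estimation step, separate analysis will be performed using the statistical method mentioned for the primary endpoint statistical analysis".
- Counts: "the numerator will include all the participants which are responders (imputed and actual responders) and the denominator will include all participants in FAS population".
- Other missing outcomes: "Missing data unrelated to ICEs, will not be imputed".

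Two other statements bear on the denominator. The supplementary strategy in SAP 14.1.1 names the Efficacy Analysis Set (EAS) as its analysis set, and SAP 5.4 defines the EAS as the part of the full analysis set (FAS) eligible for efficacy evaluation on pre-randomization information. SAP 7.2 gives a general rule that missing values are left out of the denominator when percentages are computed.

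For results after imputation, the visible text mentions back-transformed values only for the unadjusted odds ratio and CIs. The sample SAS code is not visible in the public copy.

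**The concern.** The supplementary estimand asks what the response rate would have been had nobody stopped treatment or taken prohibited medication, with missing outcomes handled as missing at random. Three groups enter the proportion: participants with an observed outcome, participants whose outcome was removed because of an ICE and then imputed, and participants with no ICE whose week 24 CRESS is simply absent. The first two are treated in line with the target. The third is not imputed, cannot enter the numerator, and remains in a denominator of all FAS participants. That is non-responder imputation by another route.

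The allocation of methods is also the wrong way round. Missing-at-random imputation is applied where missingness follows treatment failure or intolerance, and withheld where the assumption is usually easier to defend.

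Protocol 9.1 makes the study one of effect estimation with no formal hypothesis, so the estimates and their intervals are the result. With about 20 and 10 participants per arm, one participant in or out of a count is visible in the reported percentage.

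**Working it through.** **Inputs.** From SAP 3.2 and Protocol 9.5: 2:1 randomization of about 30 participants, so 20 on efgartigimod and 10 on placebo; an assumed 50% response on efgartigimod; reported placebo response of 24% to 32%. From SAP 6.6: "The default significance level will be 5%; CIs will be 95% and all tests will be two-sided". The documents give neither an ICE rate nor a rate of other missing outcomes, so both are varied below.

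**The plan's own figure.** The Wilson limits are [p + z²/(2n) ± z√(p(1-p)/n + z²/(4n²))] / (1 + z²/n). With p = 0.50, n = 20 and one-sided z = 1.645, the lower limit is (0.5677 - 0.1960)/1.1353 = 0.327. This matches the stated value of approximately 33%. The two-sided 95% interval is 29.9% to 70.1%.

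**Effect of the denominator rule.** Let p be the response rate under the estimand and k the number of participants in an arm of n with no ICE and no week 24 CRESS. If those k stay in the denominator and cannot respond, the expected proportion is p(n - k)/n, a drop of pk/n.

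- Efgartigimod, p = 50%, n = 20: k = 1 gives 47.5%, k = 2 gives 45%, k = 3 gives 42.5%, k = 4 gives 40%. The drop is 0.50 × 1/20 = 2.5 points per participant.
- Placebo, p = 24% to 32%, n = 10: k = 1 gives 21.6% to 28.8%, k = 2 gives 19.2% to 25.6%. The drop is 2.4 to 3.2 points per participant.

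Each arm's proportion can only fall, but the contrast can move either way. Taking placebo at its midpoint of 28%, the planned gap is 22 points. If 10% are missing in both arms, it becomes 45% - 25.2% = 19.8 points. If one placebo participant and no efgartigimod participant is missing, it becomes 50% - 25.2% = 24.8 points.

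**The three denominator statements side by side.** The multiple-imputation text in SAP 14.1.1 uses all FAS participants. The analysis-set line of the same strategy says EAS, as does the denominator of the as-observed fallback. SAP 7.2 would remove participants with a missing value. These give different percentages whenever the EAS is smaller than the FAS or any outcome is missing without an ICE.

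**What an unpooled interval would cost, if one were used.** With M imputations, within-imputation variance U and between-imputation variance B, Rubin's rules give r = (1 + 1/M)B/U, effective sample size n/(1 + r), and a t quantile on (M - 1)(1 + 1/r)² degrees of freedom. With M = 500, imputation from a Beta posterior within arm, and 50% response among 20:

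- 2 imputed (10%): r = 0.106, effective n 18.1, interval 29.1% to 70.9%, width 0.419.
- 4 imputed (20%): r = 0.236, effective n 16.2, interval 28.1% to 71.9%, width 0.438.
- 6 imputed (30%): r = 0.403, effective n 14.3, interval 27.0% to 73.0%, width 0.461.

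A plain Wilson interval at n = 20 has width 0.401 throughout, which is narrower by 4%, 8% and 13%. On placebo (n = 10) the figures are 4% with 1 imputed and 8% with 2.

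Simulated coverage of the plain interval at 30% response with 2 of 10 imputed is about 88% to 90%, against about 95% using the Rubin variance. The benchmark matters here. With no missing data at all, the Wilson interval at n = 10, p = 0.3 covers the truth only for 1 to 5 responders, with probability 0.121 + 0.233 + 0.267 + 0.200 + 0.103 = 92.4%. The loss due to imputation is therefore about 2 to 4 points. It is also uneven at this size: with 3 of 10 imputed, the plain interval covered 96%.

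**The case against.** **The general rule already removes missing values.** If SAP 7.2 governs, unimputed participants leave the denominator and the downward shift disappears, giving an available-case estimate, which is a recognised choice under missing at random. This is the best counter-argument, but it does not settle the matter. The rule in 14.1.1 is the specific one for this analysis and expressly puts all FAS participants in the denominator. A general output convention that says otherwise is a conflict, not a cure.

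**The statement on other missing data may belong to the fallback.** It stands after the paragraph on what happens if imputation is not feasible. Even so, that fallback puts actual responders over EAS participants, so the same participants would again count as failures.

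**Such missingness may be rare.** This is fair. A missing clinESSDAI domain, ESSPRI item or SGUS parameter voids that score, but the composite is not necessarily lost, because SAP 14.1.1 asks for response on at least three non-missing items. The documents give no rate.

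**On the interval.** A reader might infer that the supplementary Wilson interval will certainly be too narrow, computed as if imputed responses had been observed. The documents do not support that. SAP 14.1.1 describes separate analyses of the imputed datasets and a back-transformation, which implies a combining step; the code is not shown in the public copy; and a Wilson interval built on the Rubin variance would still fit Table B. What stands is that no visible sentence gives the combining rule for the proportions.

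**On importance.** A reader might also infer that this is the only check on the primary result. It is not. SAP section 2 plans IgG-stratified CMH sensitivity analyses for both estimands, and Protocol 9.3.2 plans a sensitivity analysis with missing week 24 data as non-response.

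**Conclusion.** The denominator point holds on the text of SAP 14.1.1. Any participant with no ICE and no week 24 CRESS is counted as a failure in an analysis that claims a hypothetical, missing-at-random target. The cost is 2.5 points per such participant on efgartigimod and 2.4 to 3.2 points on placebo, given the planning rates and arms of 20 and 10. The size of the shift depends on how many such participants there are, which the documents do not say, and on 14.1.1 taking precedence over SAP 7.2. The FAS/EAS mismatch needs settling whatever that number is.

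The interval is a point to confirm, not an established defect. If a plain Wilson interval were put on imputed counts, it would be about 4% to 13% too narrow with 10% to 30% of the efgartigimod arm imputed. That range is assumed, and the calculation uses a simple within-arm imputation, not the SAP's logistic model.

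Only a supplementary analysis is affected, in a proof-of-concept study whose p-values are supportive. The correction is worth making because it is cheap and the arms are small.

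**What to change.** In SAP 14.1.1, supplementary estimand:

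1. State that every missing week 24 CRESS outcome, ICE-related or not, is imputed in the same multiple-imputation model, and withdraw the sentence that excludes other missing data.
2. Name one analysis set for both numerator and denominator, in place of the present mix of EAS and FAS, and say how the general rule in SAP 7.2 applies to this analysis and to the as-observed fallback.
3. Confirm, in a sentence in Table B or 14.1.1, that each arm's proportion and its Wilson interval are pooled over the 500 datasets with Rubin's rules, for example as a Wilson interval using the Rubin total variance. If the code already does this, only the sentence is needed.

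The cost is a few sentences and, at most, a few lines of code. The downside is slightly more imputation in a supplementary analysis, and intervals that widen a little to reflect it.

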#### For the Main estimand:

Composite Variable strategy: Assessment on or after ICEs will be treated as Non responder. The rationale behind composite strategy is, discontinue of study treatment or use of prohibited concomitant medications will affect the CRESS response.

#### For the supplementary estimand:

 Document:
 Version Number:
 V2.0

 Author:
 Version Date:
 31JAN2024

 Template No.:
 CS\_TP\_BS016 Revision 7
 Reference:
 CS\_WI\_BS005

Effective Date: 01Nov2021

Statistical Analysis Plan

Page 18 of 78

Hypothetical strategy: Any early discontinuation or taking prohibited concomitant medication is observed- then the assessment will be set to missing and the missing binary outcomes will be imputed, assuming that they are missing at random. The aim of hypothetical strategy is to address the effect in an alternative hypothetical setting where subject neither discontinued or no prohibited concomitant medication available.

If the planned hypothetical approach is not feasible due to data sparsity, then available data occurring on or after ICEs will be analyzed as observed (Treatment policy). The reasoning of treatment policy is to estimate the CRESS response based on the available data and data will be analyzed as it is (regardless of the intercurrent event occurring).

For both main and supplementary estimand, additional sensitivity analysis will be performed using CMH considering IgG as stratification factor.

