# 6.3. Assignment to Study Intervention

All participants will be randomized to IMP using IRT in a 2:1 ratio of efgartigimod or placebo, respectively.

Upon confirmation of eligibility at baseline, the participant will be randomized through IRT and stratified by IgG value at screening (> 16.0 g/L or  $\leq 16 \text{ g/L}$ ).

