## 9.3.2. Primary Endpoint Analysis

The primary endpoint is response on  $\geq 3$  of 5 items of CRESS at week 24. The 5 items are systemic disease activity (clinESSDAI), patient-reported symptoms (ESSPRI), tear gland function (Schirmer's test, OSS), salivary gland function (UWSF, SGUS), and serology (serum IgG and RF).

A 95% Wilson Score CI for the proportion of CRESS responders will be presented for both treatment groups. This will be provided for all full analysis set participants and by IgG stratum at screening (> 16.0 g/L or  $\leq 16 \text{ g/L}$ ) for the efgartigimod treatment group.

Additionally, the CRESS response will be analyzed between efgartigimed and placebo using the full analysis set by means of a Cochran-Mantel-Haenszel test, stratified by IgG value at screening (> 16.0 g/L or  $\leq 16 \text{ g/L}$ ). The common odds ratio will be provided, along with the 95% CI.

In the event of missing values for the primary endpoint, only those participants who have a week 24 value will be included in the primary analysis. A sensitivity analysis, treating those participants with missing week 24 data as nonresponders, will be included.

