#### Treatment and Dosing:

Upon confirmation of eligibility at baseline, the participant will be randomized, stratified by IgG value at screening (> 16.0 g/L or  $\leq$  16 g/L).

All participants will receive efgartigimod IV 10 mg/kg or placebo once weekly for 24 weeks during the treatment period. Treatment will be administered as an approximately 1-hour IV infusion by site staff or a home nurse. The final dose will be administered at week 23.

At week 24, eligible participants may roll over to a single-arm OLE study.

Document:

Author:

Version Number:

V2.0

Version Date:

31JAN2024

Template No.: CS TP BS016 Revision 7

Reference: CS WI BS005

Effective Date: 01Nov2021

[figure not shown]
Statistical Analysis Plan

Page 20 of 78

 $This is a \ double-blinded \ study. \ The \ IRT \ will \ be \ programmed \ with \ blind-breaking \ instructions.$ 

Figure 1: Study Overview

Figure 1: ARGX-113-2106 Study Overview

ACR=American College of Rheumatology; D=day; ESSDAI=EULAR Sjögren's syndrome disease activity index; EULAR=European Alliance of Associations for Rheumatology; IV=intravenous; n=number of participants; OLE=open-label extension; pSS=Sjögren's syndrome; SS-A=anti-Sjögren's syndrome-related antigen A; SWSF=stimulated whole salivary flow (rate); UWSF=unstimulated whole salivary flow (rate); W=week

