#### Primary Analysis

Main Estimand Strategy: This is based on a composite endpoint strategy. This estimand is intended to provide an estimate of the treatment effect in the absence of prohibited concomitant medication use in a population without treatment discontinuation.

Analysis methodology: The test of proportions will be conducted at a two-sided level alpha of 0.05 with no adjustment for multiplicity. Based on the CRESS response, participants will be categorized as responders versus non-responders and a 95% Wilson Score CI for the proportion of CRESS responders will be presented for both treatment groups.

The proportion of responders and its 95% Wilson score CI will be calculated using binomial distribution. To perform this in SAS,

Document:

Author:

Version Number:

Version Date:

31JAN2024

Template No.: CS TP BS016 Revision 7

[figure not shown]
Reference: CS WI BS005

Effective Date: 01Nov2021

Statistical Analysis Plan

Page 43 of 78

The common odds ratio will be provided, along with the 95% CI. For above analysis, in the event of missing values for the primary endpoint, assessments on or after ICEs will be treated as Non-Responders as per primary estimand composite strategy.

Intercurrent events Data after study drug discontinuation and prohibited concomitant medication will be excluded and set to missing.

Missing Data not related to intercurrent events: There will be no imputation performed on missing data, not related to intercurrent events.

Document: Author: Version Number: V2.0

31JAN2024

Version Date:

Template No.: CS\_TP\_BS016 Revision 7 Reference: CS WI BS005

Effective Date: 01Nov2021

Statistical Analysis Plan

Page 44 of 78

Here, the numerator will include participants which are responders. Participants who are taking prohibited concomitant medications or early discontinue study treatment, are considered as Non-Responders. The denominator will include all participants irrespective of any ICEs occurred.

Supplementary Estimand Strategy: This is based on hypothetical strategy. Any early discontinuation or taking prohibited concomitant medication is observed- then the assessment will be set to missing and the missing binary outcomes will be imputed, assuming that they are missing at random. The aim of hypothetical strategy is to address the effect in an alternative hypothetical setting where subject neither discontinued or no prohibited concomitant medication available.

Analysis set: Efficacy Analysis set.

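### The SAP text calls the IgG-stratified CMH an additional sensitivity analysis, although the protocol makes it the only between-group analysis of CRESS response and randomisation is stratified by IgG

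*SAP*

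**What the plan says.** **Randomisation.** Protocol 6.3: "the participant will be randomized through IRT and stratified by IgG value at screening", with a cut at 16 g/L. SAP 3.1 (Treatment and Dosing) repeats it: "the participant will be randomized, stratified by IgG value at screening".

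**Protocol analysis.** Protocol 9.3.2 gives a Wilson interval for each arm. It then compares the arms "by means of a Cochran-Mantel-Haenszel test, stratified by IgG value at screening", with a common odds ratio and 95% CI. No other between-group method is named for CRESS response.

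**SAP, visible text.**
- Table B, summary measure, both estimands: "Also, CMH will be used". No stratum is given.
- Section 2, below Table B: "For both main and supplementary estimand, additional sensitivity analysis will be performed using CMH considering IgG as stratification factor".
- Section 14.1.1, main estimand: "The common odds ratio will be provided, along with the 95% CI". No stratum is given. The SAS code just before this sentence is not visible.
- Section 14.1.1, supplementary estimand: each imputed dataset is analysed by the primary-endpoint method, but the back-transformed values "will be used for reporting Unadjusted Odds Ratio and CIs".

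**The concern.** The SAP's prose gives the protocol's planned comparison the role of a sensitivity analysis, which implies that some other CMH is the main one. The natural candidate is an unstratified CMH, and the word unadjusted in the imputation section points the same way. The common odds ratio in 14.1.1 points the other way, because a single pooled table has nothing to be common across.

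This matters because the study is for estimation, without a formal hypothesis (Protocol 9.1), and is meant to inform the planning of future studies (Protocol 9.5). The odds ratio is the between-group effect estimate for the primary endpoint. A within-stratum odds ratio and a marginal odds ratio are different quantities whenever treatment has an effect and response differs by stratum, so the plan should say which one is the main result.

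**Working it through.** **Inputs.** Allocation 2:1 and about 15 participants per IgG stratum, so about 10 vs 5 in each; efgartigimod response 50% of 20; placebo response 24% to 32% (Protocol 9.5, SAP 3.2). Response rates by stratum are not given and are assumed below.

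**1. The plan's own figure.** Wilson lower limit for 10/20 with z = 1.645: centre 0.5; half-width 1.645 × sqrt(0.25/20 + 2.706/1600) / (1 + 2.706/20) = 0.173; lower limit 32.7%. This matches the stated value of about 33%. It is a single-arm figure, so the sample size does not depend on which CMH is used.

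**2. One set of totals, three odds ratios.** Take 10/20 vs 3/10 responders.
- Unstratified: (10 × 7)/(10 × 3) = 2.33. SE(log OR) = sqrt(1/10 + 1/10 + 1/3 + 1/7) = 0.822. 95% CI 0.47 to 11.7.
- Split 2/10 vs 1/5 and 8/10 vs 2/5: Mantel-Haenszel OR = [(2×4 + 8×3)/15] / [(8×1 + 2×2)/15] = 32/12 = 2.67, 95% CI 0.46 to 15.3.
- Split 2/10 vs 0/5 and 8/10 vs 3/5: (2×5 + 8×2)/(8×0 + 2×3) = 26/6 = 4.33, 95% CI 0.47 to 40.2.

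The stratified intervals use the Robins-Breslow-Greenland variance.

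**3. Exact enumeration, 10 vs 5 in each stratum.** Assumed: overall placebo rate 28% (middle of the cited range) and a common OR of (0.5/0.5)/(0.28/0.72) = 2.57. The test is the CMH chi-square without continuity correction, threshold 3.84. Each pair of results is stratified vs unstratified.

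| Placebo rate by stratum | Chance of p<0.05 | SD of log OR | ORs differ more than 1.25-fold |
|---|---|---|---|
| 28% / 28% | 20.4% vs 20.2% | 0.87 vs 0.85 | 7% of trials |
| 20% / 36% | 19.3% vs 18.4% | 0.91 vs 0.84 | 15% |
| 15% / 41% | 17.9% vs 15.4% | 0.96 vs 0.81 | 27% |

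The last two columns use trials in which both odds ratios are finite and non-zero. With no treatment effect, rejection is 4.8% vs 4.2% at 20%/36% and 4.8% vs 3.7% at 15%/41%.

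The target of the stratified analysis is 2.57 throughout. The marginal target is 2.57, then 2.48 (49.1% vs 28.0%), then 2.34 (47.7% vs 28.0%). Because the targets differ, the SDs do not rank the methods.

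**4. A wider assumption.** Hold the overall rates at 50% vs 24% and let the odds of response differ 1-, 4- or 9-fold between strata. The chance of p<0.05 is then 27.0% vs 26.8%, 28.9% vs 25.6% and 33.0% vs 24.0%. At 50% vs 32% it is 15.2% vs 15.0%, 15.8% vs 13.5% and 17.9% vs 11.7%. For comparison, the 15%/41% row above is about a 4-fold difference: (0.41/0.59)/(0.15/0.85) = 3.9.

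**The case against.** The strongest defence is that the decisive text is hidden. The method paragraph in SAP 14.1.1 breaks off where SAS code begins, and the next visible sentence is the one on the common odds ratio. In Protocol 9.3.2 the same sentence follows directly on the IgG-stratified CMH. The hidden block may name the stratum. No visible sentence states that the main CMH is unstratified, and the protocol itself introduces the stratified CMH as an addition to the Wilson intervals, so the SAP's label may be loose wording for the same analysis. This stands as far as it goes: an unstratified main analysis is not shown. Hidden code cannot repair the prose, though. If the main CMH were stratified by IgG, an additional CMH stratified by IgG would be redundant.

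A reader might infer more than the documents support:
- **That the stratum was left to be chosen at programming.** Code exists but is not visible, so this cannot be said.
- **That the change is undeclared.** The visible items of SAP 3.4 do not list it, but part of that list is not visible.
- **That the SAP ties only the STAR responder to the primary method.** SAP 14.4.1 to 14.4.3 do the same for responders at other ESSDAI, clinESSDAI and ESSPRI thresholds.
- **That an unstratified odds ratio would be materially biased.** For the main estimand, "The denominator will include all participants irrespective of any ICEs occurred", so strata can become unequal only through other missing data. With no effect and one placebo participant missing from one stratum at 15%/41%, the unstratified target is 0.93 or 1.08. For example, (4×0.15 + 5×0.41)/9 = 29.4% against 28% gives 0.93.

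The defence is also right that the numerical effect is small and that the stratified result will be produced either way.

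**Conclusion.** The point holds as a conflict in the visible text. The SAP gives the IgG-stratified CMH a secondary role, while the protocol makes it the only between-group analysis of the primary endpoint and randomisation uses the same factor. Whether the main odds ratio is in fact unstratified cannot be settled from what is visible.

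The consequence is modest. In the worked example the reported odds ratio moves from 2.33 to 2.67 or 4.33, but the unstratified interval alone runs from 0.47 to 11.7. The chance of p<0.05 differs by 0.2 to 2.5 percentage points in the main scenarios, and by up to 9 points only if the odds of response differ ninefold between strata. All of these sizes rest on assumed stratum rates. No planned sample-size figure changes, and p-values are supportive only (SAP 6.6). The reason to act is that the main estimate should be identified, should follow the protocol and should respect the randomisation groups. A gain in precision is not the reason.

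**What to change.** - In SAP Table B and 14.1.1, state that the main between-group analysis for both estimands, including multiple imputation, is the CMH stratified by screening IgG (>16.0 vs ≤16 g/L), with the Mantel-Haenszel common odds ratio and 95% CI, as in Protocol 9.3.2.
- Reword the sensitivity sentence below Table B, and replace the word unadjusted in the imputation section.
- Keep any unstratified odds ratio as a sensitivity analysis, labelled marginal.
- Apply the same method to the responder endpoints that Protocol 9.3.3 names, and only those: the clinESSDAI and ESSPRI components of CRESS, and the ESSDAI and STAR responders.

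**Cost.** SAP wording and output labels; the stratified run is already planned. With about 5 placebo participants per stratum, the stratified log odds ratio has a somewhat larger SD (0.96 vs 0.81 at 15%/41%, for different targets). It is also slightly more often zero or not estimable (3.7% vs 3.2% of trials in that scenario).
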